## 3. STUDY DESIGN

This is a Phase 2B two-site, open-label, nonrandomized 24-week study of the efficacy and safety of vismodegib (150 mg PO daily) in subjects with high risk and/or locally advanced basal cell carcinoma. A total of 36 subjects with infiltrative/morpheaform, nodular, or superficial BCC will be enrolled in the study. Each subtype group will have a minimum of 10 subjects. No group will have more than 16 subjects.

At Treatment Initiation Visit (Baseline/Day 1), eligible subjects will begin a 24-week treatment regimen with vismodegib 150 mg daily. Clinical assessments will be performed every 4 weeks during treatment. Intra-treatment tissue histopathologic evaluation will be conducted at Week 12. Subjects will be eligible to discontinue treatment early and enter the Observation period if there is no histologic evidence of tumor on Week 12 pathology specimens. Post-treatment histopathologic evaluation will be performed at Week 24 (End of Treatment visit). Subjects will be eligible to enter the Observation period in lieu of surgery if their target lesion displays complete histologic response on biopsy specimens obtained at Week 24 visit. For subjects with histologic evidence of disease on pathology at Week 24 visit, surgical excision or Mohs surgery on the target lesion will be performed within 4 weeks of the last dose of study drug. Patient Reported Outcomes (PRO) data will be collected at baseline visit, during treatment, end of treatment/early termination visit, surgical visit, and study exit (post-surgery) visit, and at first Observation period visit (when applicable) Safety assessments including adverse event (AE) monitoring and concomitant medications will be performed at each visit.

The rationale for using 24-week treatment schedule was based on previous data from pilot studies. Data from a previous trial of 33 subjects with advanced BCC, demonstrated that 94% (17/18) of responders responded by 24-weeks. (Von Hoff et al 2009) In non-responders, treatment beyond 24 weeks may unnecessarily endanger the patient and allow their basal cell skin cancer to progress potentially negatively affecting clinical outcome.

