## 9. **DATA ANALYSIS AND STATISTICAL PROCEDURES**

### 9.1 **SAMPLE SIZE DETERMINATION**

This is a pilot study to investigate efficacy of vismodegib in different histologic subtypes of BCCs. A total of 36 subjects will be enrolled into the study. The sample size for this study was selected to allow a sufficient number of subjects of histologic subtypes other than nodular BCC, the most common subtype presenting in clinical practices. Superficial BCC and infiltrative/morpheaform subtypes have similar presentation rates. The enrollment method provides assurances that that evaluable data will be available for at least 36 subjects across three subtype groups: infiltrative/morpheaform, superficial, and nodular. Refer to Section 9.2 for details on subgroup type assignment. A sample size of 16 in the nodular group yields a 95% confidence interval of 54%-96% for an observed partial response rate. The nodular group is

included as part of the pilot study, in part, to assess the overall viability of the study. It is important to note that response rate of approximately 75% is anticipated in the nodular group, based on the published literature; the sample size of 16 the nodular group is sufficient to detect this level of efficacy. A sample size of 10 for the infiltrative/morpheaform and superficial BCC groups yields a 95% confidence interval of 10%-70%. Although the confidence intervals are wide, the sample sizes are sufficient to detect a response rate greater the null rate (0%), the expected efficacy level if the treatment had no effect in these histologic subtypes.

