#### 9.3.3 **Efficacy Analysis**

##### 9.3.3.1 **Analysis of Primary Endpoints**

#### 9.3.3.1.1 **Clinical Response**

Comparison of dimensions of tumor within debulk specimen at surgery visit with dimensions of post-biopsy tumor as drawn on template at screening visit will be assessed by a t-test for independent samples.

Sub-group analyses by histologic subtype will be conducted by demographic factors including: gender, race, and anatomic location of target lesion will also assessed for any independent association with clinical response. Statistical significance was defined by alpha 0.05. All analysis was performed using SPSS (PASW) version 18.

Analysis of the following subgroups will be performed:

- Nonaggressive subtypes vs. Aggressive subtypes
- Clinical subtypes (infiltrative/morpheaform, nodular, and superficial)

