#### 9.3.3.1.2 **Histologic response**

Chi-square analysis will be performed to assess histologic response of residual tumor and area of tumor clearance for all tumors and by histologic subtype.

Comparison of the “invasion index” on biopsy specimen and excision specimen will be assessed by a t-test for independent samples.

Histologic subtypes observed on biopsy specimen and excision specimen will be depicted in a frequency table and proportions of each histologic subtype will be compared using a t-test for dependent samples.

Size estimate of tumor based on biopsy specimen to actual size of tumor specimen on day of surgical excision or Mohs surgery will be assessed by a t-test for independent samples.

Location and depth of specific tumor cells of each histological subtype on biopsy and surgical specimen.

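### The pooled chi-square test of histologic response names no comparator or null, and on each plausible reading it is either uninformative about clearance or ignores within-lesion pairing

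*Combined protocol and SAP*

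**What the plan says.** The design has one regimen and no control: "This is a Phase 2B two-site, open-label, nonrandomized 24-week study" (Section 3). Histologic response is one of the two primary endpoints (Section 9.3.1), and its analysis is given in Section 9.3.3.1.2: "Chi-square analysis will be performed to assess histologic response of residual tumor and area of tumor clearance for all tumors and by histologic subtype". That section gives no null proportion, reference group, time point or layout for the table. The significance level stands in the neighbouring Section 9.3.3.1.1: "Statistical significance was defined by alpha 0.05".

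Four other places bear on how the sentence might be read:

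- Section 2.1 makes comparison between histologic subtypes the primary objective. The subtype half of the sentence serves it.
- Section 9.3.1.2 defines the residual-tumor endpoint as histologic change relative to the pre-treatment biopsy. It treats clearance of the clinically clear area as a separate assessment.
- Inclusion criterion 5 in Section 4.1 requires histologically confirmed BCC, so every target lesion is tumor-positive at entry.
- Section 9.1 contains the only null rate in the documents, 0%, in its discussion of the two groups of 10: "the null rate (0%), the expected efficacy level if the treatment had no effect in these histologic subtypes".

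**The concern.** A chi-square test needs groups to compare or a stated set of expected proportions. The subtype half has the first. The pooled half has neither on the page, so two analysts could run different tests and both follow the plan.

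The analysis is of a primary endpoint. A pooled p-value below 0.05 would naturally be read as evidence that the drug clears tumor histologically. If the test run is one that answers a different question, or one that treats two specimens from one lesion as independent, that reading would be wrong.

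**Working it through.** **Inputs**

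- 36 subjects (Section 9.1, "A total of 36 subjects will be enrolled into the study"), with one target lesion each for the primary analysis (Section 9.2). All 36 are assumed evaluable unless stated otherwise.
- Alpha 0.05 (Section 9.3.3.1.1). Sidedness is not stated; two-sided is assumed.
- 0 of 36 lesions clear before treatment (Section 4.1, criterion 5).
- The documents give no expected histologic clearance rate, so the counts below are illustrative.

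**The plan's own figures.** None is given for the chi-square test. The intervals in Section 9.1 reproduce as Wald intervals, p ± 1.96·√(p(1−p)/n):

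- 12/16: 0.75 ± 1.96·√(0.75·0.25/16) = 0.75 ± 0.212, or 53.8% to 96.2% (stated: 54%-96%).
- 4/10: 0.40 ± 1.96·√(0.40·0.60/10) = 0.40 ± 0.304, or 9.6% to 70.4% (stated: 10%-70%; the 40% is inferred as the midpoint).

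So the plan justifies its size by interval widths, not by power for this test.

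**Reading (a): one sample against an equal split.** With k of 36 cleared, X² = 2·(k−18)²/18 = (k−18)²/9 on 1 df.

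- k = 12 or 24: 36/9 = 4.00, p = 0.0455.
- k = 7: 121/9 = 13.4, p = 0.0002.
- k = 18: 0, p = 1.00.
- k = 20: 4/9 = 0.44, p = 0.50, although the exact 95% interval for 20/36 (56%) is 38% to 72%.

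Clearance of one third and of two thirds gives the same p-value. Using 0% as the null does not help: the expected cleared count is 36 × 0 = 0, and the statistic is undefined.

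**Reading (b): residual site against clearance site.** Sections 6.1.3 and 6.1.4 assign both assessments to lesions with partial response or stable disease, so the specimens are paired. One site is biopsied because tumor is visible or palpable, the other because the skin looks clear. Suppose 20 lesions give both, with tumor in 18 residual and 8 clearance specimens:

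- Pearson X² = 40·(18·12 − 2·8)²/(20·20·26·14) = 10.99, p = 0.0009.
- Exact McNemar for the three possible discordant splits: 10/0, p = 0.002; 11/1, p = 0.006; 12/2, p = 0.013.

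All are significant, yet 8/20 = 40% of the apparently clear areas still hold tumor. The test mainly reflects how the sites were chosen.

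**Reading (c): before against after in the same lesion.** With 0 clear before and k clear after, uncorrected Pearson gives X² = 72k/(72−k). Exact McNemar, with no reverse changes, gives p = 2·0.5^k.

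| k of 36 | X² | Pearson p | Pearson p, continuity-corrected | Exact McNemar p |
|---|---|---|---|---|
| 3 | 3.13 | 0.077 | 0.238 | 0.250 |
| 4 | 4.24 | 0.040 | 0.123 | 0.125 |
| 5 | 5.37 | 0.020 | 0.064 | 0.0625 |
| 6 | 6.55 | 0.011 | 0.033 | 0.031 |

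At 4 and 5 cleared, uncorrected Pearson is significant and the paired test is not. From 6 upward both are below 0.05. The continuity correction nearly closes the gap here, but the plan does not ask for it.

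**The subtype half.** With groups of 16, 10 and 10 (within the limits in Section 3), a common rate of 40% gives expected counts of 4 and 6 in a group of 10. A rate of 75% gives 7.5 and 2.5. Some expected counts can therefore fall below 5.

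**The case against.** The strongest reply is that a comparison does exist for all tumors together. Section 9.3.1.2 refers residual tumor to the pre-treatment biopsy, and Section 4.1 fixes the baseline as tumor-positive, so a before/after p-value does carry evidence about clearance. A Week 12 against Week 24 comparison is also conceivable. This stands, and it rules out saying that the pooled p-value tells us nothing on any reading. It does not rescue the planned test: Section 9.3.3.1.2 names neither comparison, and both are paired.

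Three further objections also stand:

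- Even against 50%, the result read with its direction says whether clearance is above or below half. It is a poorly motivated benchmark, but not one wholly unrelated to efficacy.
- A reader might infer that the equal-split null contradicts the 0% in Section 9.1. The documents do not support that. The 0% concerns response in the two groups of 10, not pooled histologic clearance, and the 50% is an assumption made here.
- A reader might infer that pairing overturns the site comparison. It does not in the example. That example also scores tumor as present or absent, whereas Section 9.3.1.2 defines the residual-tumor endpoint as any histologic change.

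Finally, this is a pilot whose primary objective is the subtype comparison, and no decision rule rests on the pooled p-value. That limits the consequence.

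**Conclusion.** The point holds for the pooled half of the sentence only. As written, it applies a chi-square test with no stated comparator or null. Under reading (a) the p-value measures distance from an unstated 50%. Under (b) it compares paired sites that were selected to differ. Under (c) it addresses clearance but uses an unpaired test, which changes the conclusion at 4 or 5 of 36 cleared (p = 0.040 and 0.020, against 0.125 and 0.0625). Even a valid before/after test could not attribute clearance to vismodegib without a control.

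The sizes rest on 36 evaluable target lesions, two-sided alpha 0.05 taken to apply to this section, illustrative counts and, for (c), no continuity correction. The data themselves are unharmed, and the subtype comparison remains the right one for the primary objective. The issue is moderate and should be corrected before analysis.

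**What to change.** In Section 9.3.3.1.2:

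- Confine the chi-square sentence to the comparison between subtypes by removing its reference to all tumors together. Specify an exact test where expected counts are below 5.
- For all target lesions together, one per subject, report two results separately: the number and percentage with histologic change in residual tumor, and the number and percentage with histologic clearance in the clinically clear area. Take each over the lesions that have that specimen, with an exact or Wilson 95% interval. With 36 lesions, exact intervals would be, for example, 6/36 = 17% (6% to 33%), 18/36 = 50% (33% to 67%) and 30/36 = 83% (67% to 94%).
- If a within-lesion comparison is wanted, name it, use the exact McNemar test and label it descriptive.

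This needs a few sentences of wording and no extra subjects or data. The small downside is that the pooled result carries no p-value. Reporting by interval fits the way Section 9.1 justifies the sample size.

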### 9.3.3.2 **Analysis of Secondary Endpoints**

#### 9.3.3.2.1 **Onset of Efficacy**

For each target lesion, interval to clinical response and best overall response will be recorded and a histogram depicting response to treatment will be created. For subjects who discontinue treatment early due to disease progression or personal preference, interval of treatment will be recorded.

#### 9.3.3.2.2 **Safety and Tolerability**

Graded adverse events (number and percent) will be reported according to the National Cancer Institute’s Common Terminology Criteria for Adverse Events (version 4.0). (See Appendix X.) Adverse events that lead to early discontinuation of treatment will also be tabulated.

Percentage of patients able to complete 24-week treatment regimen will be recorded. For patients that are unable to complete 24-week treatment regimen, average and median time of treatment will be assessed.

#### 9.3.3.2.3 **Patient Reported Outcomes**

Quality of life (QoL) during study participation and patient impression of adverse effect tolerability will be assessed.

QoL will be assessed using patient reported outcomes (PRO) questionnaires at Baseline, Week 8, Week 16, and Week 24 study visit/End of treatment visit using the following validated measures:

- FACT-G (v. 4), Functional Assessment of Cancer Therapy-General (Appendix VIII)
- Skindex-16, a quality-of-life measure for patients with skin disease (Appendix VI.)

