### 2.2 SECONDARY OBJECTIVES

- To evaluate the onset of efficacy of vismodegib during 24 weeks of treatment in various histologic subtypes of high risk and/or locally advanced basal cell skin cancer
- To evaluate the safety and tolerability of vismodegib over 24 weeks of treatment in subjects with high risk and/or locally advanced basal cell skin cancer
- To evaluate patient reported outcome (PRO) measures during 24 weeks of treatment with vismodegib in subjects with high risk and/or locally advanced basal cell skin cancer

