### 6.1.2 Interval Visits

The objectives of these interval visits are to provide a systematic and objective evaluation of the target tumor, and to monitor subject safety while ensuring continued compliance with study procedures. Every attempt should be made to have individual subject assessments performed by the same physician (investigator or equally qualified physician listed on FDA form 1572), preferably on the same day of the week for each visit.

The following procedures will be performed at all visits during treatment:

- Assessment of any changes (deletions, additions, or dose modifications) to medications.
- Complete physical examination including general appearance, skin exam, and visual inspection of target lesion(s).
- Vital signs (BP; heart or pulse rate; and oral, tympanic, or temporal temperature).
- Weight and height measurements.
- Urine pregnancy test ( $\alpha$ -hCG) only for women who are of childbearing potential.
- laboratory evaluation to evaluate abnormalities in hematocrit/platelet counts, renal or hepatic function and electrolytes if deemed necessary by the investigator.
- Photography and measurement of target lesion with ruler visible in photographic field
- Template map drawing of clinically evident tumor margins and local landmarks using a permanent marker on a clear plastic overlay.
- Adverse Event (AE) Monitoring.
- Review subject dosing diary and conduct accountability of used and unused study drug returned by the subject to determine study drug dosing regimen compliance.
- Collect unused study drug and re-dispense study drug
- Observe subject administer doses of study drug and document in the dosing diary.
- Clinical Response Evaluation by investigator (See below Section 6.2.2, Clinical response evaluation of target lesion for instructions)
- Reminder to use effective measures to avoid pregnancy
- Remind subjects to bring all unused drug supplies with them to their next scheduled visit.

Week 8, 16, and 24, Surgery Visit, Study Exit Visit (Post-Surgery Visit): PRO questionnaires will be performed by the subject (SKINDEX-16 and Functional Assessment of Cancer Therapy – General (FACT-G). (Appendix 7 and 9.)

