At week 12, Intra-treatment tissue histopathologic evaluation will be performed to assess histologic response. For subjects with apparent clinical complete response at Week 12 and no histologic evidence of disease is observed, subjects will enter the observation period and be followed clinically every 3 months up to one year (See Appendix 5, Figure 3 for more

information). Sample diagrams demonstrating the sites of screening biopsies and Week 12 biopsies for a tumor is seen in Section 6.1.3.

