#### 6.1.8 **Observation period**

All subjects will be followed for the observation period of 1 year after discontinuation of study medication.

During the observation period the subjects will followed every 3 months for 1 year after last dose.

The following study procedures during observation period:

- Assessment of any changes (deletions, additions, or dose modifications) to medications.
- Complete physical examination including general appearance, skin exam, and visual inspection of target lesion(s) area.
- Vital signs (BP; heart or pulse rate; and oral, tympanic, or temporal temperature).
- Weight and height measurements.
- Urine pregnancy test ( $\alpha$ -hCG) only for women who are of childbearing potential for visits within 7 months of last dose of study drug.
- Photography and measurement of target lesion area
- Adverse Event (AE) Monitoring.
- Reminder to use effective measures to avoid pregnancy (for women who are of child bearing potential for visits within 7 months of last dose of study drug).
- PRO questionnaires will be performed by the subject (SKINDEX-16 and Functional Assessment of Cancer Therapy – General (FACT-G) at first visit during Observation period (3 months after discontinuing treatment).

If a subject is noted to have a recurrence of target lesion or new lesions suspicious for BCCs on any part of the body, biopsy will be performed to confirm diagnosis. If pathology is consistent with basal cell carcinoma, the subject will exit the Observation period and all treatment options

will be discussed with the subject. If Mohs micrographic surgery is determined to be the best therapeutic option, surgical excision and study procedures will be performed as described in Section 6.1.6.

Subjects who underwent surgical excision of the target lesion may elect to be followed by phone contact every 3 months to provide information on the status of the surgical site and occurrence of any adverse events.

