## Subjects with complete clinical response and complete histologic response at Week 12 visit

	Pre-study Screening Visit	Treatment Initiation Visit	Visit 2	Visit 3	Visit 4	Observation Visit 1	Observation Visit 2	Observation Visit 3	Observation Visit 4
	Day 0	Baseline / Day 1	Week 4	Week 8	Week 12	Week 24	Week 36	Week 48	Week 60
Description									
Informed Consent	X								
Medical History	X								
Inclusion/Exclusion	X								
Concomitant medications	X	X	X	X	X	X	X	X	X
Physical exam	X	X	X	X	X	X	X	X	X
Vital signs	X	X	X	X	X	X	X	X	X
Height, weight	X	X	X	X	X	X	X	X	X
Target lesion identification	X								
Lesion measurement (pre-biopsy)	X								
Lesion measurement (post-biopsy)	X								
Lesion photography	X	X	X	X	X	X	X	X	X
Tumor margins and local landmarks map	X	X	X	X	X	X	X	X	X
Lesion punch biopsy/biopsies	X				X				
Urine Pregnancy Test	X 	X	X	X	X	X	X	X	X
CMP?CBC Tests	X	X 	X 	X 	X 				
Patient reported outcome questionnaires		X		X		X			
Review subject diary			X	X	X				
Study drug instructions		X	X	X	X				
Reminder to use effective measures to avoid pregnancy	X	X	X	X	X	X	X		
Administer study drug		X	X	X	X				
Adverse Events (AE) monitoring - PI and Oncologist		X	X	X	X	X	X	X	X

1. Two negative pregnancy tests with a sensitivity of at least 25 mIU/mL prior to starting medication. These tests must be at least 19 days apart. For patients with regular menstrual cycles, the second pregnancy test should be done during the first 5 days of the menstrual period immediately preceding the beginning of therapy and after the patient has used 2 forms of contraception for 1 month. For patients with amenorrhea, irregular cycles, or using a contraceptive method that precludes withdrawal bleeding, the second pregnancy test must be done immediately preceding the beginning of therapy and after the patient has used 2 forms of contraception for 1 month.
2. Repeat testing after screening test is at the discretion of the investigator as clinically determined
3. Post surgical subjects will be offered observational follow up as office visits or telephone visits

14.7            **APPENDIX 7: SKINDEX-16**

[http://www.proqolid.org/instruments/skindex\\_skindex\\_skindex\\_29\\_skindex\\_16](http://www.proqolid.org/instruments/skindex_skindex_skindex_29_skindex_16)

Thank you for participating in this study. We appreciate it. Please see below for instructions during your study participation.

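### Subjects who stop drug at Week 12 for complete response have no questionnaire scheduled at their last treatment visit, and the plan does not say how their off-drug Week 24 score is handled

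*Combined protocol and SAP*

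**What the plan says.** Section 2.2 sets the secondary objective: "To evaluate patient reported outcome (PRO) measures during 24 weeks of treatment with vismodegib". Section 3 says of patient-reported outcomes (PROs) that "data will be collected at baseline visit, during treatment, end of treatment/early termination visit", and then adds the surgical visit, the exit visit and, where applicable, the first observation visit.

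Section 6.1.2 (Interval Visits) gives the timing during the study: "Week 8, 16, and 24, Surgery Visit, Study Exit Visit (Post-Surgery Visit): PRO questionnaires will be performed by the subject". Week 12 is not listed. The same section contains the early-stopping rule: "For subjects with apparent clinical complete response at Week 12 and no histologic evidence of disease is observed, subjects will enter the observation period". Section 6.1.8 schedules one set of questionnaires in that period, "at first visit during Observation period (3 months after discontinuing treatment").

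Appendix 6 has a separate table for this pathway, titled "Subjects with complete clinical response and complete histologic response at Week 12 visit". Its questionnaire row is marked at Baseline, Week 8 and Observation Visit 1 (Week 24). The Week 12 cell is empty.

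For the analysis, Section 9.3.3.2.3 names "questionnaires at Baseline, Week 8, Week 16, and Week 24 study visit/End of treatment visit". It says nothing about treatment status at each time point.

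**The concern.** For a subject who stops at Week 12 on complete response, Week 12 is the last treatment visit. The schedule leaves that visit without a questionnaire although Section 3 asks for one at end of treatment. A score not collected there cannot be recovered.

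The later questionnaire cannot stand in for it. FACT-G (Appendix 9) asks about the past seven days and includes an item on being bothered by treatment side effects. Answered about 12 weeks after the last dose, it does not describe life on the drug, which is what the objective and the tolerability aim of Section 9.3.3.2.3 are about.

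The off-drug questionnaire also falls in the same calendar week as the full-course subjects' end-of-treatment questionnaire. An analyst working by week label could put the two in one column, and Section 9.3.3.2.3 gives no rule against it.

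**Working it through.** The plan states no figure to reproduce here; the check is of the visit schedule. Inputs are the questionnaire rows of the three Appendix 6 tables, read against their column headings.

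| Pathway (Appendix 6) | Questionnaires marked | Post-baseline, on treatment | First one after treatment ends |
|---|---|---|---|
| Complete response at Week 12 | Baseline, Week 8, Week 24 (Observation Visit 1) | 1 (Week 8) | Week 24 |
| Complete response at Week 24 | Baseline, Weeks 8, 16, 24, Week 36 (Observation Visit 1) | 3 (Weeks 8, 16, 24) | Week 36 |
| Surgery after Week 24 | Baseline, Weeks 8, 16, 24, Surgery, Study Exit | 3 (Weeks 8, 16, 24) | Surgery Visit |

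1. **End of treatment.** Week 12 stoppers have no questionnaire there. The other two pathways have one at Week 24.

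2. **Time off drug at Observation Visit 1.** Week 12 stoppers: 24 − 12 = 12 weeks. Week 24 complete responders: 36 − 24 = 12 weeks. The visit is tied to stopping drug, and only for the Week 12 stoppers does it land on Week 24. The 12 weeks is the scheduled interval. The table still marks study drug at the Week 12 visit, so the gap is slightly shorter if dosing continues until the pathology is back.

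3. **Whether another rule fills the gap.** Section 6.1.5 applies the Week 24 procedures to subjects who leave the study early, and names patient decision and disease progression as the reasons. Stopping on complete response is neither, and these subjects remain in the study.

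4. **Baseline.** The Treatment Initiation Visit lists only SKINDEX-16, while Section 9.3.3.2.3 lists both instruments at Baseline. If the visit list is followed, Week 8 is the only FACT-G these subjects complete before stopping.

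5. **Possible off-drug share at calendar Week 24.** Share = k / 36, where k is the number stopping at Week 12 and 36 is the planned total (Section 9.1). The documents give no k, so the values below are assumptions, with every subject supplying a score:
   - 2/36 = 5.6%
   - 4/36 = 11.1%
   - 9/36 = 25.0%
   - 12/36 = 33.3%

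**The case against.** **No passage plans to pool the two kinds of score.** A reader might infer that the plan will merge off-drug with on-drug scores and so make 24 weeks of drug look better tolerated than it is. The documents do not support this. Section 3 lists the first observation visit separately from end of treatment, Section 6.1.8 ties its questionnaire to time since stopping, and Appendix 6 labels it an observation visit. This objection stands: what remains is silence in Section 9.3.3.2.3, not a planned bias.

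**End of treatment may mean each subject's own last treatment visit.** Week 12 would then be covered by Section 3, and the blank cell would be a flowchart omission. This is arguable, but Section 3 itself says "Post-treatment histopathologic evaluation will be performed at Week 24 (End of Treatment visit"), and Section 6.1.4 equates the two in its title. On either reading the text and the table must be reconciled.

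**The stoppers are not lost to the PRO analysis.** A reader might infer that they have no questionnaire at all after Week 8. They do have Observation Visit 1, and Section 9.3.3.2.3 covers quality of life during study participation. One who recurs and has surgery may also complete the Surgery and Study Exit questionnaires. What they lack is an on-treatment score after Week 8.

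**The size is unsupported.** The only complete-response count in the documents is 2 of 33 (2/33 = 6.1%) in the Phase I trial of Section 1.3. That trial enrolled metastatic or locally advanced disease and followed it over 20 months, so it does not settle the Week 12 rate here, but it gives no support for a large one. A reader might also expect distortion between histologic subtypes, but Section 9.3.3.2.3 plans no subtype comparison of PROs.

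**Using Week 12 as an end-of-treatment score would mix 12-week and 24-week exposure.** This is fair, and the change below keeps the two apart.

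**Conclusion.** The gap is real and is visible in the plan's own tables. Subjects who stop at Week 12 for complete response have one on-treatment post-baseline questionnaire instead of three and none at their last treatment visit, contrary to the general statement in Section 3 and short of the objective in Section 2.2. Their next scheduled questionnaire falls at calendar Week 24, about 12 weeks off drug, and Section 9.3.3.2.3 does not say how to treat it. A calendar-week summary could therefore mix the two kinds of score, although nothing in the documents says that it will.

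The size is unknown because the share stopping at Week 12 is not given. The 5.6% to 33.3% range rests wholly on assuming 2 to 12 stoppers among 36 with complete data, and the true effect may be small. This is a secondary endpoint in a pilot study. The point is a worthwhile, inexpensive improvement and does not threaten the primary analysis.

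**What to change.** - **Schedule.** Add SKINDEX-16 and FACT-G at Week 12 for all subjects, in Section 6.1.2 (Interval Visits) and in all three Appendix 6 tables, completed before the Week 12 biopsies. Collecting from everyone is necessary because the histology that decides early stopping is not yet known at that visit.
- **Analysis, Section 9.3.3.2.3.** State that for subjects who stop at Week 12, the Week 12 score is reported as their last on-treatment PRO, labelled as 12 weeks of exposure and not merged with the 24-week scores. State that Observation Visit 1 questionnaires are reported separately as off-treatment data, whichever calendar week they fall in.
- **Wording.** Reconcile the use of end of treatment in Sections 3 and 9.3.3.2.3 with the Appendix 6 table for Week 12 responders, and the Baseline instrument list at the Treatment Initiation Visit with Section 9.3.3.2.3.

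The cost is two short self-completed forms at an existing visit and a few sentences of text. The downside is slightly more subject burden at Week 12. No treatment rule changes.
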